7.1.2. Trial Endpoints

Efficacy Endpoints

The efficacy endpoints are defined, as follows:

- Technical Success, defined as a combination of A0 ablations (complete tumor ablation with a surrounding 5 mm margin) and A1 ablations (complete tumor ablation with inadequate margins) based on contrast-enhanced MRI performed up to 7 days following the original ablation procedure.
- Technical Efficacy, defined as a combination of A0 ablations (complete tumor ablation with a surrounding 5 mm margin) and A1 ablations (complete tumor ablation with inadequate margins), based on contrast-enhanced MRI scans at 1 month (+/- 7 days) after the original ablation procedure.
- Local tumor progression (LTP), evaluated at every visit after the ablation of the target tumor(s). LTP describes the appearance of tumor foci at the edge of the ablation zone, after at least one contrast-enhanced follow-up MRI scan has documented adequate ablation and an absence of viable tissue in the target tumor and surrounding ablation margin by using imaging criteria.
- Secondary efficacy rate, defined as the percentage of tumors that have undergone successful repeat ablation following identification of local tumor progression at any time during study follow up.
- Progression-free survival, defined as length of time from the original ablation procedure until any type of disease progression (i.e. local or distant).
- Overall survival measured from the time of the original ablation procedure to the time of death or last follow-up if death has not occurred.

Confidential Page 26 of 61

Safety Endpoint

The safety endpoint is the rate of AEs and SAEs reported at each analysis and cumulatively throughout the entire study period.

Patient Reported Outcomes:

- Pain, as measured by Numeric Pain Rating Scale, before the ablation procedure (measured at Screening Visit), post ablation (within 7 days after ablation]), and at the 1-month follow-up visit.
- Quality of Life, as measured by EORTC QLQ-C30 and liver-specific EORTC QLQ-HCC18, before the ablation procedure (measured at Screening Visit), post ablation (within 7 days after ablation), and at each follow-up visit.

Health Economics:

 Health economics associated with the ablation procedure, including complete procedure time, ablation time, number of ablations, number and types of probes, change in probe position, number of computed tomography (CT) and ultrasound scans performed for probe and margin assessment, and length of hospital stay.

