7.2.4. Study Procedures

Screening

Patients will be consented prior to any actual study-specific screening procedures being conducted. Patients will be considered enrolled into the study upon satisfaction of the following criteria:

- Completion of the informed consent process and signing the Informed Consent Form (ICF).
- Verification of the eligibility criteria (Section 7.1) by the Principal Investigator (PI) and/or authorized investigators. The verification must be conducted by the PI and/or authorized investigators prior to performing any study-related procedure or completing any form associated with this study.

Screening Failures

Screened patients who are not enrolled will be considered screen failures. For patients who are determined to be screen failures, only the following data will be recorded on the eCRF:

- Informed consent date.
- Demographic information (age, race, gender, and ethnicity).
- Reason for screening failure.

Randomization

This is a single-arm study. Hence, there will be no control or comparison group, and therefore no need for randomization.

Visit 1 – Baseline/Screening Visit

The following screening activities will occur within 14 days of the study's original ablation procedure:

- The patient must be given ample time to review and sign the ICF.
- Collect demographic information (year and month of birth, sex, race, ethnicity).
- Review and collect medical, surgical, and radiation histories, including alcohol
 consumption and hepatitis, if applicable. Note: HCC diagnosis does not need to be
 reported as medical history.
- Review inclusion/exclusion criteria and determine if the patient is eligible for participation.
- Pain, using the Numeric Pain Rating Scale (NPRS).
- Quality of Life questionnaires: EORTC QLQ-C30 and liver-specific EORTC QLQ-

Confidential Page 36 of 61

HCC18.

- At minimum, an MRI of the liver must be taken at Baseline/Screening (per each study site's SOC) to ascertain tumor type, location, and size (measured in longest diameter and the diameter that is perpendicular to this longest diameter). The MRI must be taken within 14 days prior to ablation (Visit 2A). Ultrasound and/or CT are optional.
- Laboratory tests must be performed within 14 days prior to ablation (Visit 2A);
 otherwise the test(s) must be repeated.
 - Coagulation tests (PT, APTT, and INR).
 - Liver function tests (AST, ALT, GGT, albumin, indirect, direct and total bilirubin, and total protein).

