8.1.3 Baseline

Unless otherwise specified, baseline is defined as the last non-missing measurement taken prior to the date of initial ablation (Day 0) (including unscheduled assessments). Ultrasound and/or CT scan on Day 0 is taken prior to ablation, and is considered baseline (including unscheduled assessments).

Change from baseline will be defined as the difference between the post-baseline value at the point of interest and the baseline value.

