8.3.2 Baseline Target Tumor Assessement (Analyzed on tumor level)

Baseline target tumor assessment will be summarized for FAS and Run-in

In "[Target Tumor Assessments]" CRF page, maximum tumor dimension, tumor type and vertical dimension be summarized, same as other continuous measurement for each target lesion. Counts for liver segment and major vessel assessment will be tabulated at baseline.

Other details on Target tumor assessments will only be listed, sorted by phase, site, subject, target tumor.

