8.4.1 Effectiveness Endpoint(s)

All effectiveness endpoints will be summarized for FAS and PPS. Subjects in run-in analysis set will be also summarized for technical success and technical efficacy endpoints.

The effectiveness endpoints are defined, as follows:

Technical Success

Technical Success, defined as a combination of A0 ablations (complete tumor ablation with a surrounding 5 mm margin) and A1 ablations (complete tumor ablation with inadequate margins) based on contrast-enhanced MRI performed at Visit 2B (up to 7 days following the original ablation procedure).

The number and percentage of tumors achieving Technical Success will be summarized. Percentage will be calculated relative to the total count of evaluable target tumor lesions at Visit 2B. A 95% confidence interval will be estimated using wald method. The number and percentage of tumors with A0, A1 and A2 margins will be presented as a sub-categorization :

Note: Ablation evaluation by Investigator is collected in "Ablation Zone Assessment" CRF page. A0: complete tumor ablation with adequate margin (surrounding 5 mm margin) A1: complete tumor ablation with inadequate margins

A2: Incomplete tumor ablation

A subject archieving technical success is defined as a subject with all tumors reaching A0 or A1 at Visit 2B. The number and percentage of subjects archieving Technical Success will be summaried as well. Percentage will be calculated relative to the total number of subjects in relavent analysis population (FAS or PPS). A 95% confidence interval will be estimated using wald method.

Number and percentages of reasons for A1 and A2 ablation categorization will be also summarized.

Technical Efficacy

Technical Efficacy, defined as a combination of A0 ablations (complete tumor ablation with a surrounding 5 mm margin) and A1 ablations (complete tumor ablation with inadequate margins), based on contrast-enhanced MRI scans at Visit 3 (1 month +/- 7 days) after the original ablation procedure.

Tumor-level analysis method is same as that of primary endpoint. The number and percentage of tumors achieving Technical Efficacy will be summarized and a 95% confidence interval will be estimated using Wald method. The number and percentage of tumors with A0 and A1 margins will be presented as a sub-categorization within each presentation of Technical Efficacy, as well as a summarization for the number and reasons for repeat ablations through Visit 3.

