A subject archieving technical efficacy is defined as a patient with all tumors reaching A0 or A1 at Visit 3. The number and percentage of subjects archieving Technical Efficacy will be summaried as well. Percentage will be calculated relative to the total number of subjects in relavent analysis population (FAS or PPS). A 95% confidence interval will be estimated using wald method. But the subjects who have any A2 margin since the visit 2B scan would not be counted as technical efficacy regardless if the tumor was corrected with repeat ablation.

Local tumor progression (LTP) (the 2nd interim, final)

LTP is evaluated after the ablation of the target tumor(s). LTP describes the appearance of tumor foci at the edge of the ablation zone, after at least one contrast-enhanced follow-up

MRI scan has documented adequate ablation, and an absence of viable tissue in the target tumor and surrounding ablation margin, by using imaging criteria.

Tumor-level analysis method is same as that of Technical Success endpoint. The number and percentage of tumors with LTP will be summarized and a 95% confidence interval will be estimated using Wald method.

A subject with LTP is defined as a patient with any target tumor LTP. The number and percentage of subjects with LTP. Percentage will be calculated relative to the total number of subjects in relevant analysis population (FAS or PPS).

Subgroup analysis is defined in SAP section 8.11. Two subgroup columns (subjects/tumors with only initial ablation and subjects/tumors with repeat ablation) and 1 total column will be used as analysis columns in LTP tables.

Tumor type (primary HCC and recurrent HCC and other) will be another subgroup variable for LTP (analyzed for patient level and tumor level).

LTP start date is the date of initial ablation of a subject. The event date of LTP is collected in "Ablation Zone Assessment" CRF page as following table:

		Event/Censoring	
	Situation	Date	Outcome
No post-base	eline or no baseline Ablation Zone A	ssessment	
	No post-baseline local tumor	Date of initial	
A1	evaluation	ablation	Censored
	No baseline local tumor	Date of initial	
A2	evaluation	ablation	Censored
With baselin	e and post-baseline tumor assessm	ents	
	Local Tumor Progression and zero or one missed tumor assessment prior to confirmed		
B1	LTP	Date of first LTP date	Event

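### SAP Table 3 row A2 censors at the ablation date any subject without a 'baseline' local tumour evaluation, which conflicts with the LTP definition and protocol 8.6; only the Kaplan-Meier LTP analysis is affected

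*SAP*

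**What the plan says.** SAP 8.4.1 sets the LTP clock at the initial ablation and gives event and censoring rules in Table 3. Row A2 of that table (not to be confused with the A2 margin category) covers subjects with "No baseline local tumor" evaluation and censors them at the date of initial ablation. The subheading over rows A1 and A2 includes the words "or no baseline Ablation Zone A" (the last word is Assessment). The only event rows, B1 and B2, stand under a second subheading that requires both a baseline and a post-baseline assessment.

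Four other places bear on this:

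- **Meaning of baseline.** Under SAP 8.1.3, unless otherwise specified, "baseline is defined as the last non-missing measurement taken prior to the date of initial ablation (Day 0"). Table 3 specifies nothing different.
- **LTP definition.** Protocol 7.1.2 counts tumour foci at the edge of the ablation zone that appear "after at least one contrast-enhanced follow-up MRI scan has documented adequate ablation and an absence of viable tissue". SAP 8.4.1 repeats this.
- **Available assessments.** Before ablation there is a screening MRI: "The MRI must be taken within 14 days prior to ablation (Visit 2A") (protocol 7.2.4). SAP 8.3.2 also states that "Baseline target tumor assessment will be summarized for FAS and Run-in". The Ablation Zone Assessment form records the A0, A1 or A2 result of the ablation, and in the protocol's Schedule of Activities the first evaluation of that kind is at Visit 2B.
- **Censoring in the protocol.** Protocol 8.6 analyses observed data only. In the final analysis it censors patients who have had no event, at their last known visit.

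**The concern.** A subject censored at time zero is in no risk set. If such a subject later has a documented LTP, neither the event nor the follow-up enters the Kaplan-Meier rates or curve. Nothing in the LTP definition calls for this, because the definition depends on a scan taken after ablation, and any follow-up MRI that documents adequate ablation will serve.

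The wording also leaves the programmer to choose a meaning. The subheading points to the ablation zone form, which describes something that exists only after ablation. SAP 8.1.3 points to a time before ablation. The two do not fit together. A programmer who follows the form would probably take Visit 2B as the reference. A subject who missed that MRI but was clear at Visit 3 would then lose up to 36 months of valid follow-up.

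LTP rates are the efficacy result named for the 12-month analysis (protocol 8.1, SAP 8.6), so the rule affects a main output.

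**Working it through.** **Step 1. Sample size, from the plan.** Protocol 8.2.1 wants 100 patients with one-year data and allows 20% dropout: 100 / 0.80 = 125. Adding 4 sites × 3 run-in patients gives 125 + 12 = 137, which matches the plan. The main-phase figure of 125 is used below. The plan gives no figure for the effect of row A2.

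**Step 2. What the row does under each meaning of baseline.**

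| Meaning | Fits | Share of subjects caught |
|---|---|---|
| Screening MRI or target tumour assessment | SAP 8.1.3 and the row's own words | Near 0, since the MRI is mandatory |
| Visit 2B ablation zone assessment | The subheading, but not SAP 8.1.3 | The share missing that scan (not given) |

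Under either meaning, an LTP documented later in a caught subject is not counted as an event.

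**Step 3. Subjects lost on the Visit 2B meaning.** The missing share f is an assumption: 125 × 0.03 = 3.75 (about 4), 125 × 0.05 = 6.25 (about 6), 125 × 0.10 = 12.5 (12 to 13).

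**Step 4. Events lost.** For illustration, take a constant LTP hazard from the multicentre Chinese series cited in protocol 4.1.1, which had 78 LTPs in 1363 tumours over a mean of 17.3 months. (The protocol prints 5.9%, but 78/1363 = 5.7%; the count is used.) Applying a per-tumour rate to subjects is a simplification.

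- Hazard = −ln(1 − 78/1363) / 17.3 = 0.0589 / 17.3 = 0.00341 per month.
- 12 months: 1 − exp(−0.00341 × 12) = 4.0%, or 5.0 events in 125.
- 36 months: 1 − exp(−0.00341 × 36) = 11.5%, or 14.4 events in 125, ignoring dropout.
- Events removed = 125 × f × cumulative rate. At f = 5%: 0.25 by 12 months and 0.72 by 36 months. At f = 10%: 0.50 and 1.44.

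**Step 5. Precision at 12 months.** The 95% half-width is 1.96 × √(0.040 × 0.960 / n). It is 3.44 percentage points at n = 125, 3.53 at n = 118.75 (f = 5%) and 3.62 at n = 112.5 (f = 10%).

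**Step 6. Shift in the 12-month Kaplan-Meier estimate.** This was simulated with 2000 runs of 125 subjects, the hazard above and 20% dropout by 12 months. A fraction f was set to censored at time zero.

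| f | Missingness unrelated to LTP | Three times likelier in subjects with LTP by 36 months |
|---|---|---|
| 5% | about 4.0%, no shift | 4.0% falls to 3.7% |
| 10% | about 4.0%, no shift | 4.0% falls to 3.4% |

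**Step 7. Scope.** SAP 8.4.1 also reports the number and percentage of tumours and of subjects with LTP. Those summaries make no reference to Table 3, so the row does not touch them. The same subject could therefore be an LTP case in the crude count and censored at day zero in the curve.

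**The case against.** The strongest defence is that the row is almost empty. It speaks of a local tumour evaluation, not of an ablation zone. The screening MRI is mandatory, and tumour number and size are inclusion criteria, so a treated subject with no pre-ablation evaluation would be a rare deviation. This reading agrees with SAP 8.1.3. The Visit 2B reading does not, and SAP section 4 labels that visit as post-ablation. The study is also descriptive, with no hypothesis and no acceptance threshold, and the shifts in the working are small.

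Most of this stands, and it limits the size of the point. It does not justify the row: on the screening reading the row does nothing useful, and in the few subjects it catches it still drops any LTP they have.

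A reader might go further than the documents allow in three ways:

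- **That all 125 subjects are censored at day zero,** because no ablation zone exists before ablation. This takes the subheading literally, ignores the row's own words and would leave rows B to E with nobody in them. It shows that the subheading is loose, not that data will be lost on that scale.
- **That observed LTPs vanish from the results.** They would leave the Kaplan-Meier analysis only.
- **That the loss is informative.** A missed early scan might reflect a complicated course, but nothing in the documents establishes this. The threefold ratio is a what-if.

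**Conclusion.** Row A2 is wrong as written. It conflicts with the LTP definition, which needs only a qualifying post-ablation MRI. It also conflicts with protocol 8.6, which in the final analysis censors only patients without an event. Its subheading does not fit the SAP's own definition of baseline. Whenever the row applies, it gives the wrong result for the Kaplan-Meier LTP rates and curve.

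The practical effect runs from near zero (screening MRI) to small or moderate (Visit 2B assessment). On the Visit 2B reading, 5% to 10% missing removes about 0.7 to 1.4 of 14.4 illustrative events by 36 months. The 12-month rate shifts only if missingness is linked to LTP, by about 0.3 to 0.6 percentage points at the assumed threefold ratio, in the device's favour. These figures rest on assumed missing-scan rates and on a hazard borrowed from the cited series. The conflict between the passages does not depend on either.

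**What to change.** In SAP Table 3:

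1. Delete row A2, and remove the reference to a missing baseline from the subheading over rows A1 and A2. Row A1 (no post-ablation assessment, censored at ablation) remains.
2. Change the second subheading to 'With post-ablation tumor assessments', so that rows B to E apply to every subject with at least one post-ablation local assessment.
3. Keep the date of initial ablation as the time origin, and state that an LTP counts once any post-ablation MRI has documented adequate ablation.
4. State how subjects whose scans never document complete ablation are handled. They have post-ablation scans, so row A1 does not cover them. Left unstated, they would fall into row C and count as LTP-free follow-up.

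Align the Table 4 subheadings for consistency only: Table 4 has no row for a missing baseline, so no PFS rule changes.

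The cost is SAP wording, which protocol 8.7 allows for through an amended SAP. No data collection, visit or sample size changes.

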06 AUGUST 2020, VERSION: 4.0

- Length of hospital stay.
- Complete tumor ablation evaluation.
- Any update to relevant concomitant medications.
- Relevant concomitant procedures.
- All AEs and SAEs.

Post Ablation Follow-up Visits 3 to 11 (End of Study)

The following data will be collected post ablation at the post ablation follow-up visits, from Visit 3 through the end of the study (Visit 11), as follows:

- Pain score, using the NPRS (Visit 3 only).
- Quality of Life questionnaires: NPRS pain score, EORTC QLQ-C30 and liver-specific EORTC QLQ-HCC18.
- MRI of the liver.
- Laboratory tests.
 - Coagulation tests (PT, APTT, and INR).
 - Liver function tests (AST, ALT, GGT, albumin, indirect, direct and total bilirubin, and total protein).
 - o Renal function test (Urea, creatinine, and electrolytes [sodium, potassium, and chloride]).
 - Complete blood count (differential cell count and platelet count).
 - Alpha-fetoprotein (AFP) test.
- ECOG performance status.
- Complete tumor ablation evaluation (Visit 3 only)
- Local tumor progression (LTP) to be evaluated by a study physician based on MRI imaging. All MRI scans are to be submitted to the Sponsor.
- Progression-free survival to be evaluated by a study physician based on MRI imaging or may be reported by a patient's primary treating oncologist, if different than the study physician. If there is a progression, the study physician should specify if the progression is of the original target tumor, a new HCC tumor in the liver, or a distant metastasis.
- Any update to relevant concomitant medications.
- Relevant concomitant procedures.
- All AEs (if within 30 days post an ablation procedure).
- All SAEs through end of study.

Confidential Page 39 of 61 06 AUGUST 2020, VERSION: 4.0

Note: Repeat ablations may be performed on target tumor(s) only.

Unscheduled Visits

The following data will be collected at all unscheduled visits:

- Reason for the unscheduled visit.
- Relevant concomitant medications.
- Relevant concomitant procedures.
- AEs (if within 30 days post an ablation procedure) and all SAEs.

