	Local Tumor Progression and over one missed tumor assessment prior to confirmed	Date of the latest evaluable local tumor assessment prior to the missed	
B2	LTP	assessment	Event
		Date of last local	
		tumor assessment	
	No progression, either alive or	with no documented	
С	death	LTP	Censored

Table 3: Censoring Rules for LTP

		Date of last tumor assessment with no documented	
D	Dead	progression	Censored
		Date of last tumor	
		assessment with no	
		documented	
E	Withdrawal by Subject	progression	Censored

Local tumor progression rates at 3, 6, 9, 12, 18, 24, 30, and 36 months will be estimated using the Kaplan-Meier (K-M) method and 95% confidence intervals (Greenwood's formula) will be provided.

The K-M curve of time to LTP will be provided.

Secondary efficacy rate (the 2nd interim, final)

Secondary efficacy rate is defined as the percentage of subjects whose tumors have undergone successful repeat ablation following identification of local tumor progression at any time during study follow up.

It could be found in CRF page, Ablation Zone Assessment, "Re-ablate with Neuwave". For subgroup that has LTP and used Certus to re-ablate, the number and percentage of subjects achieving secondary efficacy, will be summarized and a 95% confidence interval will be estimated using wald method.

Progression-free survival (PFS) (the 2nd interim, final)

PFS is defined as length of time from initial ablation until disease progression.

Table	e 4. Censoring Rules for PFS		
	Situation	Event Date	Outcome
No po	st-baseline or no baseline Ablation Zo	ne Assessment	
	No post-baseline tumor evaluation		
A1	and alive	Date Ablation performed	Censored
	No post-baseline tumor evaluation		
	but died on or before the second		
A2	scheduled tumor assessment	Date Ablation performed	Censored
With baseline and post-baseline tumor assessments			

Table 4: Censoring Rules for PFS

В	Any Tumor Progression and zero or one missed tumor assessment prior to progression	Date of first progression	Event
		Date of last progression	
	PD happens after >=2 consecutively	assessment before	
С	missing tumor assessment	missing assessments	Censored
		Date of last progression	
		assessment with no	
D	No progression	documented progression	Censored

Progression-Free Survival rate will be estimated using the Kaplan-Meier method and 95% confidence intervals (Greenwood's formula) will be provided for 6, 12, 18, 24, 30, 36 months.

The K-M curve of time to progression will be provided.

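### SAP Table 3 (LTP censoring): the rows for death and withdrawal overlap the other rows, are not limited to subjects without LTP, and use a date based on any progression instead of LTP

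*SAP*

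**What the plan says.** SAP 8.4.1, Table 3, assigns each subject an LTP date and outcome.

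- **Row B1**, "Local Tumor Progression and zero or one missed tumor assessment prior to confirmed" LTP: event at the first LTP date.
- **Row B2**, "Local Tumor Progression and over one missed tumor assessment prior to confirmed" LTP: event, dated at the latest evaluable local assessment before the gap. Neither B row has a condition about what happens to the subject afterwards.
- **Row C**, "No progression, either alive or" dead: censored. The date begins "Date of last local" and refers to the tumor assessment without documented LTP.
- **Row D**, labelled only as dead: censored at the "Date of last tumor assessment with no documented" progression.
- **Row E**, "Withdrawal by Subject": censored, with the same date wording as row D.

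The SAP gives no order of precedence among the rows. Elsewhere, progression is wider than LTP. Protocol 7.2.4 asks the study physician to state whether the "progression is of the original target tumor, a new HCC tumor in the liver, or a distant metastasis", and protocol 7.1.2 defines PFS on local or distant progression.

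Protocol 8.6 has its own censoring rule. In the final analysis, subjects without an event are censored at their last known visit date. At an interim analysis, a continuing subject is censored at the database lock unless the endpoint has already occurred.

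**The concern.** Rows D and E raise two problems.

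1. **Different date.** They drop the word local and replace LTP by progression. A subject with non-local progression and no LTP would then be censored at a date that depends on whether he or she later leaves the study, not on when the ablation zone was last seen clean.
2. **Overlap.** They carry no condition that LTP is absent. A subject with LTP who later dies or withdraws matches a B row (event) and also D or E (censored).

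The trial tests no hypothesis and has no acceptance threshold. Protocol 8.4 says that performance will be judged from all the data in the context of other therapies, so the estimates are themselves the result. LTP is the effectiveness output that SAP 8.6 names for the 12-month analysis. Two programmers could follow Table 3 faithfully and obtain different Kaplan-Meier LTP rates.

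**Working it through.** **Step 1. The rows applied to four subjects** (scans at 1, 3, 6, 9, 12, 18, 24, 30 and 36 months).

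| Subject | B1 | C, reading progression as LTP | D as worded |
|---|---|---|---|
| No progression of any kind, dies at month 20 | – | censored, month 18 | censored, month 18 |
| New liver tumor at month 6, no LTP to month 18, dies at month 20 | – | censored, month 18 | censored, month 3 |
| LTP at month 6, dies at month 20 | event, month 6 | – | censored, month 3 |
| New liver tumor at month 6, no LTP, still in study | – | censored, last LTP-free scan | does not apply |

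Row E gives the same dates as row D if death is replaced by withdrawal. If progression in row C instead means any progression, the fourth subject fits no row. The first subject is unaffected on every reading.

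**Step 2. The plan's own figures.** The documents give no number for the LTP rules. Enrolment reproduces: 100/(1 − 0.20) = 125, and 125 + 4 × 3 = 137. The 125 main-phase subjects are used below to scale counts.

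**Step 3. Inputs for an illustration** (not planning values).

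- LTP: protocol 4.1.1 cites 5.9% at a mean follow-up of 17.3 months. Hazard = −ln(1 − 0.059)/17.3 = 0.003515 per month, so 36-month LTP = 1 − exp(−36 × 0.003515) = 11.9%. The cited rate is per tumor (78/1363) and is used here as a patient-level hazard. The printed fraction is in fact 5.7%, which would give about 11.5%.
- Death: cited 3-year survival of 72.5%. Hazard = −ln(0.725)/36 = 0.00893 per month.
- Assumed: non-local progression of 20–60% and withdrawal of 0–20% by 36 months. The upper withdrawal value is the plan's dropout allowance. All times are independent and exponential.

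**Step 4. Kaplan-Meier LTP at 36 months**, 1 − ∏(1 − d/n) over the scan times, with d the LTP events and n the number at risk.

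| Reading of Table 3 | 36-month LTP |
|---|---|
| B rows first, all others censored at the last LTP-free scan | 11.9% |
| B rows first, D/E dates taken literally for leavers without LTP | about 12.0–12.5% |
| D/E override B | about 9.8–10.8%, with about 13–23% of LTP events lost |

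The second reading biases the rate upward even though LTP, death and withdrawal are independent. Events among leavers are all kept, while observed event-free time is removed from the risk sets.

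**Step 5. Sensitivity.** A second set of runs used a hazard of 0.059/17.3 and let the death hazard be one or three times as high after progression.

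- First reading 11.2–11.7%, second 11.4–12.1%, third 8.0–10.5%.
- Within a scenario, the second reading adds about 0.1–0.7 points and the third removes about 1.0–3.3.
- Per 125 subjects, about 3–19 are censored early under the second reading. Under the third, about 2–4 of 11–12 events are lost.
- If 36-month LTP is assumed to be 20%, the three ranges are 19.4–20.1%, 19.8–21.1% and 14.1–18.1%.

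**The case against.** A reader might infer that the LTP result of anyone who dies or withdraws is erased or back-dated. The documents do not support that.

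- **Erasure is not the planned rule.** It requires rows D and E to override B1 and B2, which no passage says. Protocol 8.6 reserves final-analysis censoring for subjects without an event, and protocol 7.1.5 says that data collected up to withdrawal will be considered for analysis. This stands as evidence of intent. It does not put the rule into Table 3. Protocol 8.6 also names a different date, the last known visit, so it cannot settle row C against rows D and E.
- **The wording may be shorthand.** Row C describes its situation as no progression but dates it by LTP, so progression may mean LTP throughout the table. Rows D and E would then give the same date as row C and nothing would be back-dated. This reading is possible. It makes D and E redundant, still leaves their overlap with B unstated, and departs from the wider meaning of progression in the protocol.
- **Few subjects are exposed.** Only those with LTP, or with earlier non-local progression, who then die or withdraw are affected. The crude number and percentage with LTP are not tied to Table 3. Both points stand.
- **The effect is small against the precision.** With 125 subjects and 11.9%, the 95% half-width without any censoring is 1.96 × √(0.119 × 0.881/125) = 5.7 points. That is larger than the shift under either reading in the base illustration. However, the shift is systematic and avoidable, whereas the interval reflects sampling error.

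**Conclusion.** The point holds as a defect of Table 3 as written. Rows D and E duplicate row C, are not limited to subjects without LTP, use a date on a different endpoint, and have no stated precedence. On the likelier reading, with B1 and B2 taking precedence, the literal D/E dates raise the illustrated 36-month Kaplan-Meier LTP rate only slightly, from 11.9% to about 12.0–12.5%. If D and E overrode B, the rate would fall to about 9.8–10.8%; this is a gap in the table that protocol 8.6 argues against, not a rule the plan adopts. The overlap and the change of wording are certain from the text. The sizes rest on a published per-tumor LTP rate used as a patient-level constant hazard, on a published survival figure, and on assumed rates of non-local progression and withdrawal. The point should be corrected, but it does not threaten the trial's conclusions on the likelier reading.

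**What to change.** In SAP Table 3:

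1. Delete rows D and E, or limit both to subjects without LTP and give them row C's date.
2. Reword row C along these lines: *No LTP (alive, dead or withdrawn): censored at the last local tumor assessment with no documented LTP.*
3. Add a sentence that B1 and B2 take precedence over any later death or withdrawal, consistent with protocol 8.6.
4. Note that Table 3's assessment-based censoring date replaces the last known visit date of protocol 8.6 for this endpoint. Protocol 8.7 allows such a change to be recorded in an amended SAP.

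The cost is SAP wording and one derivation rule. No new data are needed and the sample size of 137 does not change.
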